12.2 GHOSTWRITING AND GUEST/GHOST AUTHORSHIP

Ghostwriting, guest authorship, and ghost authorship are strictly prohibited. The contribution of a writer, which, when performed under the direction of the author(s), is considered a form of specialized, technical assistance, is acknowledged in the earliest draft in which the writer is involved.

12.3 DETERMINING ORDER OF AUTHORSHIP

Author order is determined by mutual agreement at the earliest possible time, with due consideration to overall contributions to the study, to the publication, or to scientific knowledge of the subject matter.

ANNEX 1. LIST OF STAND-ALONE DOCUMENTS

List of Advisory Board members

ANNEX 2. ENCEPP CECKLIST FOR STUDY PROTOCOLS

A copy of the ENCePP Checklist for Study protocols available at website: encepp.eu/standards_and_guidances/index.html completed and signed by the main author of the study protocol should be included in Annex 2.

The checklist will facilitate the review of the protocol and evaluation of whether investigators have considered important methodological aspects.

In question 9.5 of the Checklist, Revision 1:

“Study start” means “Start of data collection”

“Study progress” means “Progress report(s)”

“Study completion” means “End of data collection”

“Reporting” means “Final report of the study results”

See attached file

ANNEX 3. ADDITIONAL INFORMATION

None.

| Table 46. Patients' satisfaction for medical treatment (TSQM-9 subscales) at each study visit- Switchers vs non-switchers | 61 |
| 6 QUALITY CHECKS ON THE STATISTICAL REPORT | 62 |
| 7 REVISION HISTORY | 64 |
| 8 APPENDICES..... | 65 |
| 8.1 COPD awareness questionnaire scoring system..... | 65 |
| 8.2 Modified Medical Research Council (mMRC) dyspnoea scale | 67 |
| 8.3 Treatment Satisfaction Questionnaire for Medication (TSQM-9)..... | 68 |
| 8.4 COPD Assessment Test (CAT) | 72 |
| 8.5 Brief Illness Perception Questionnaire (B-IPQ)..... | 74 |
| 8.6 Morisky Medication Adherence Scale (MMAS-4)..... | 76 |

LIST OF ABBREVIATIONS

| | |
|--------|--|
| ACOS | Asthma COPD Overlap Syndrome |
| ADR | Adverse Drug Reaction |
| AE | Adverse Event |
| BI | Boheringer Ingelheim Italy S.p.A |
| B-IPQ | Brief-Illness Perception Questionnaire |
| BMI | Body Mass Index |
| BS | Biostatistician |
| CAT | COPD Assessment Test |
| CDM | Clinical Data Manager |
| COPD | Chronic Obstructive Pulmonary Disease |
| DLCO | Diffusion Lung Capacity for carbon monoxide |
| eCRF | electronic Case Report Form |
| ER | Emergency Room |
| FAS | Full Analysis Set |
| FEV1 | Forced Expiratory Volume in the 1 st second |
| FVC | Forced Vital Capacity |
| ICS | Inhaled corticosteroids |
| ICU | Intensive Care Unit |
| LABA | Long-acting β 2-agonists |
| LAMA | Long-acting muscarinic agonists |
| Max | Maximum |
| Min | Minimum |
| MMAS-4 | Morisky medication Adherence Scale, 4 items |
| mMRC | modified Medical Research Council dyspnea scale |
| N | Number of observations |
| NA | Not Available |
| NK | Not Known |
| PDE4-I | Phosphodiesterase type 4 inhibitors |
| PRO | Patient-Reported Outcome |
| R-DMS | Responsible Data Management and Statistics Unit |
| SABA | Short-acting β -agonists |
| SAE | Serious Adverse Event |
| SAMA | Short-acting muscarinic agonists |
| SAP | Statistical Analysis Plan |
| SD | Standard Deviation |
| TLC | Total Lung Capacity |
| TSQM-9 | Treatment Satisfaction Questionnaire for Medication, 9 items |
| VC | Vital Capacity |

1 STATISTICAL ANALYSIS PLAN OBJECTIVES

The *SATisfaction and adherence to COPD treatment* study (i.e. SAT study) is a multi-center, non-interventional (observational) cohort study based mainly on newly collected data. About 400 consecutive COPD patients will be enrolled in approximately 8 months (from first patient enrolled). Patients will be followed up for 1 year, with an intermediate evaluation after 6 (+/-1) months from baseline (which is compatible with current clinical practice in Italy for COPD patients management).

The present Statistical Analysis Plan has been designed considering the following input documents:

- the Study Protocol v.1.0 31/07/2015,
- the electronic case report form v. 1.2 27/04/2016;
- the minutes of the Customer's Meeting held on the 26/06/2017.

This SAP is aimed at evaluating the following SAT study objectives:

Primary objective:

To describe the patients' satisfaction to COPD medical treatments (by means of the TSQM9) during a 12-month observation period (namely, at enrolment, and after 6 and 12 months) in real- world setting.

Secondary objectives:

1. To describe patient disease perception (by means of illness perception questionnaire B-IPQ), adherence to COPD treatment (by means of MMAS4), health status (by means of CAT questionnaire) and dyspnea (by means of mMRC) during a 12-month observation period.
2. To analyze the relation between treatment satisfaction and demographic (such as age, gender), clinical (such as number of exacerbations, spirometric parameters) parameters and PROs during a 12-month observation period.
3. To describe the health care resources utilization and related cost according to the Italian National Health Service (INHS) during a 12-month observation period.
4. To assess the correlation between patients' satisfaction and resource utilization.

In this document the eCRF fields are indicated as follows: "label of the field" [*name of the eCRF form.name of the variable in the dataset*].

2 DEFINITION OF EVALUABLE PATIENTS

2.1 Patients evaluable at enrolment (FULL ANALYSIS SET)

All enrolled patients meeting the following inclusion / exclusion / other criteria listed in the present paragraph will be considered evaluable at enrollment (Full analysis set) (i.e. COPD patients aged ≥ 40 years, with stable pharmacological treatment for COPD and no exacerbations for at least 3 months, who signed informed consent and privacy form, with at least one Treatment Satisfaction Questionnaire for Medication (TSQM-9) domain score calculated at enrollment visit):

Inclusion criteria

Criterion 1: Patients aged ≥ 40 years

- Question "1. Is the patient aged ≥ 40 years?" = "Yes" [\[F01_INC_EXC_CRITERIA.CI_1\]](#) AND
- Inclusion criterion "1. Patients aged ≥ 40 years?" not checked in the PROTOCOL DEVIATION FORM [\[F24_PROTOCOL_DEVIATION_FORM.PD_CI_1\]](#) AND
- Age at enrollment visit (years) ≥ 40 [\[_PatientInfo.Age\]](#)

Criterion 2: Patients must have a documented diagnosis of chronic obstructive pulmonary disease (COPD)

- Question "2. Has the patient a documented diagnosis of chronic obstructive pulmonary disease (COPD)?" = "Yes" [\[F01_INC_EXC_CRITERIA.CI_2\]](#) AND
- Inclusion criterion "2. Patients must have a documented diagnosis of chronic obstructive pulmonary disease (COPD)" not checked in the PROTOCOL DEVIATION FORM [\[F24_PROTOCOL_DEVIATION_FORM.PD_CI_2\]](#) AND
- Date of COPD diagnosis (mm/yyyy) not missing [\[F04_COPD_MEDICAL_HISTORY.MH_Date_diagnosis\]](#)

Criterion 3: Patients with no exacerbations in the last 3 months

- Question "3. Patient without any exacerbation in the last 3 months" = "Yes" [\[F01_INC_EXC_CRITERIA.QUESTION_3.CI_3\]](#) AND
- Inclusion criterion "3. Patients with no exacerbations in the last 3 months" not checked in the PROTOCOL DEVIATION FORM [\[F24_PROTOCOL_DEVIATION_FORM.PD_CI_3\]](#) AND
- Onset dates at each follow-up visit (Row 1 to 10) [\[F08_EXACERBATIONS.Ex_exacer_1-10_onset_date\]](#) > Date of enrolment visit (dd/mm/yyyy) [\[_PatientInfo.Date_enrollment\]](#)

Criterion 4: Patients requiring regular treatment according to GOLD guidelines, i.e.: undergoing stable pharmacological treatment for COPD since at least 3 months

- Question "4. Does the patient require a regular treatment according to GOLD guidelines, i.e.: undergoing stable pharmacological treatment for COPD since at least 3 months?" = "Yes" [\[F01_INC_EXC_CRITERIA.CI_4\]](#) AND
- Inclusion criterion "4. Patients requiring regular treatment according to GOLD guidelines, i.e.: undergoing stable pharmacological treatment for COPD since at least 3 months" not checked in the PROTOCOL DEVIATION FORM [\[F24_PROTOCOL_DEVIATION_FORM.PD_CI_4\]](#) AND
- COPD Pharmacological therapy form: Start date of therapy (dd/mmm/yyyy) not missing AND (Start date of therapy (dd/mmm/yyyy) [\[F20_COPD_PHARMACOLOGICAL_THERAPY.START_DATE_THER\]](#) < Date of enrolment visit (dd/mm/yyyy) - 3*30.4375 [\[_PatientInfo.Date_enrollment\]](#) OR Start date of therapy (dd/mmm/yyyy) > Date of enrolment visit (dd/mm/yyyy)) AND
- COPD Pharmacological therapy form: End date of therapy (dd/mmm/yyyy) [\[F20_COPD_PHARMACOLOGICAL_THERAPY.END_DATE_THER\]](#) = missing OR End date of therapy (dd/mmm/yyyy) > Date of enrolment visit (dd/mm/yyyy) [\[_PatientInfo.Date_enrollment\]](#)

Criterion 5: Written informed consent to both participation in the study and privacy form

- Question "5. Is a written informed consent to both participation in the study and privacy form available?" = "Yes" [\[F01_INC_EXC_CRITERIA.CI_5\]](#) AND
- Inclusion criterion "5. Written informed consent to both participation in the study and privacy form" not checked in the PROTOCOL DEVIATION FORM [\[F24_PROTOCOL_DEVIATION_FORM.PD_CI_5\]](#) AND
- Date of informed consent signature (dd/mm/yyyy) not missing [\[_PatientInfo.Date_CI\]](#) AND
- Date of privacy form signature (dd/mm/yyyy) not missing [\[_PatientInfo.Date_privacy\]](#) AND
- Date of informed consent signature (dd/mm/yyyy) = Date of privacy form signature (dd/mm/yyyy) AND
- Date of informed consent signature (dd/mm/yyyy) ≤ Date of enrolment visit (dd/mm/yyyy)

Criterion 6: Patients capable of discernment and able to read or write in Italian language

- Question "6. Is the patient capable of discernment and able to read or write in Italian language?" = "Yes" [\[F01_INC_EXC_CRITERIA.CI_6\]](#) AND
- Inclusion criterion "6. Patients capable of discernment and able to read or write in Italian language" not checked in the PROTOCOL DEVIATION FORM [\[F24_PROTOCOL_DEVIATION_FORM.PD_IC_6\]](#)

Exclusion criteria**Criterion 7: Patients who are currently participating in a clinical trial on experimental drugs**

- Question "7. Does the patient currently participate in a clinical trial on experimental drugs?" = "No" [\[F01_INC_EXC_CRITERIA.EC_1\]](#) AND
- Exclusion criterion "1. Patients who are currently participating in a clinical trial on experimental drugs" not checked in the PROTOCOL DEVIATION FORM [\[F24_PROTOCOL_DEVIATION_FORM.PD_EC_1\]](#)

Criterion 8: Patients naïve to pharmacological treatment for COPD

- Question "8. Is the patient naïve to pharmacological treatment for COPD?" = "No" [\[F01_INC_EXC_CRITERIA.EC_2\]](#) AND
- COPD Pharmacological therapy form: Start date of therapy (dd/mm/yyyy) (earliest record) not missing AND
- Exclusion criterion "2. Patients naïve to pharmacological treatment for COPD" not checked in the PROTOCOL DEVIATION FORM [\[F24_PROTOCOL_DEVIATION_FORM.PD_EC_2\]](#)

Criterion 9: Diagnosis of Asthma COPD Overlap Syndrome (ACOS)

- Question "9. Does the patient have a diagnosis of Asthma COPD Overlap Syndrome (ACOS)?" = "No" [\[F01_INC_EXC_CRITERIA.EC_3\]](#) AND
- Exclusion criterion "3. Diagnosis of Asthma COPD Overlap Syndrome (ACOS)" not checked in the PROTOCOL DEVIATION FORM [\[F24_PROTOCOL_DEVIATION_FORM.PD_EC_3\]](#)

Other criteria**Criterion 10: patients with at least one Treatment Satisfaction Questionnaire for Medication (TSQM-9) domain score calculated at enrollment visit**

- TSQM-9 items #1,2,3 [\[TSQM9_1-3\]](#) not missing & ≠ "Non risponde" at enrollment visit, OR
- TSQM-9 items #4,5,6 [\[TSQM9_4-6\]](#) not missing & ≠ "Non risponde" at enrollment visit, OR
- TSQM-9 items #7,8,9 [\[TSQM9_7-9\]](#) not missing & ≠ "Non risponde" at enrollment visit

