| Eligibility criteria Inclusion and exclusion criteria, Informed consent and privacy form | X | | |
| Baseline information (Socio-)demographic variables: age, gender, race, geographic location, housing situation, marital status, educational and employment status | X | | |
| Weight, body mass index | X | X | X |
| Physical examination | X | X | X |
| Life Habits Smoking (yes/no, number of pack/years, smoke duration) | X | X | X |
| Medical History and concomitant diseases. - Charlson Comorbidity Index. | X | X | X |
| COPD medical history: Date of COPD diagnosis (years from diagnosis); n° of COPD exacerbations/year during the previous year to enrolment visit | X | | |
| Functional assessment Lung function test results (FEV1, FVC, FEV1 % of the predicted, RV, TLC,DLCO) according to clinical practice | X | X | X |
| CAT questionnaire | X | X | X |
| COPD Exacerbations** after enrollment Onset and resolution date Severity (mild, moderate, severe) | X | X | X |
| Disease severity (GOLD 2015 Guidelines) | X | X | X |
| Medications related to COPD, COPD exacerbations and adverse events (LABA, LAMA, SABA, SAMA, ICS/LABA, steroids, antibiotics, etc.): drug, dose, frequency, duration of therapy. - Long-Term Oxygen Therapy (liquid and/or concentrate). | X | X | X |
| Change of therapy during observation period and reason for change. | | X | X |
| Non Pharmacological treatment - Pulmonary rehabilitation- | X | X | X |
| Health-care resource consumption related to COPD, COPD | X | X | X |

| Study Visits | Visit 1 | Visit 2 | Visit 3 |
|--|----------|-----------------|-------------------|
| | Baseline | Follow-up | Follow-up 2 |
| Months | 0 | 6 (+/-1) | 12 (+/- 1) |
| exacerbations and adverse events: 
 • Drugs • hospitalization (inward and day hospital) • emergency room access • outpatient visits • GP visits • laboratory tests • clinical examinations | | | |
| Patient Reported Outcomes Questionnaires/scales | | | |
| TSQM-9 | X | X | X |
| MMRC (modified MRC dyspnea scale) | X | X | X |
| CAT | X | X | X |
| MMAS-4 (Morisky Medication-Taking Adherence Scale) | X | X | X |
| Brief Illness Perception Questionnaire | X | X | X |
| Awareness structured interview | X | X | X |
| S(AE) assessment | | X | X |

Table 1. Recorded variables.

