9.7 DATA ANALYSIS

Descriptive analysis will be means, medians, quantiles, proportions (with their respective 95% confidence intervals and SE when relevant) and contingency tables according to the nature of the variables. As a dispersion measurement the standard deviation and the interquartile range will be calculated.

Statistical analysis will be performed using the SAS software.

The statistical analysis will be done on all evaluable patients i.e. patients who enter the study without inclusion-exclusion criteria violations and with at least one TSQM-9 domain score (effectiveness, convenience and global satisfaction) calculated. Enrolled patients not evaluable for analysis will be described in terms of frequency of violations and according main socio-demographic variables (such as age and gender), clinical (such as disease severity and number of exacerbations in the 12-month before enrollment) and treatment satisfaction scores (if available) at baseline.

Patients with missing values will not be excluded from the analysis, their data will not be replaced; frequency of missing data will be given for all analyzed variables. Lost to follow up patients will be analyzed until their last available visit.

Appropriate descriptive statistics for main socio-demographic (gender, age, race, education and employment status, smoking habits) and clinical variables (medical history for COPD and not, disease severity and awareness) at baseline visit will be presented to describe the study population at inclusion. Patients at inclusion in the study will be also described in terms of ongoing pharmacological and non pharmacological treatments for COPD.

Moreover, the study population will be described in terms of number of exacerbations occurred during study period and changes in COPD medication since baseline.

The study objectives will be evaluated as below described.

Primary objective

The patients' satisfaction for medical treatment will be assessed by the 9-item Treatment Satisfaction Questionnaire for Medication (TSQM-9) at each study visit (45, 46). TSQM-9 is a self-rated tool for evaluating patient satisfaction to medical therapy. It is composed by 3 domains covering efficacy, convenience and global treatment satisfaction. TSQM-9 scores will be calculated according to author's instructions and summarized at each time point on all evaluable patients. Patients lost to follow up will be considered until their last available visit.

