2.4 Safety set

All enrolled patients meeting the inclusion criteria #4 and #5 and not meeting the exclusion criteria #7, #8 and #9 (i.e. all enrolled subjects who provided informed consent to both participation in the study and privacy form, requiring regular treatment according to GOLD guidelines) will be included in the safety analysis.

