4 CONTENTS

The analyses will be performed on the Analysis set specified for each table.

Missing data will not be imputed and so patients with missing data will be excluded from the analyses of that variable(s).

If the investigator is unable to collect the requested information the data will be “NK” (Not Known) or “NA” (Not Available), if the investigator did not record the information the data will be “Not Recorded”.

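### SAP Criterion 2 drops a patient with a confirmed COPD diagnosis from the Full Analysis Set when only the diagnosis date is blank

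*SAP*

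**What the plan says.** SAP 2.1 builds the FAS from a list of criteria that must all hold: "All enrolled patients meeting the following inclusion / exclusion / other criteria listed in the present paragraph will be considered evaluable at enrollment". Criterion 2 has three parts joined by AND: the investigator answers yes to a documented COPD diagnosis, the matching box on the deviation form is unticked, and "Date of COPD diagnosis (mm/yyyy) not missing".

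SAP 2.2 and 2.3 require FAS membership for the 6- and 12-month sets. Chart 1 assigns the satisfaction, other PRO, regression, resource-use, correlation and exacerbation analyses to these three sets.

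The protocol's diagnosis criterion (item 2 in the Abstract, item 8 in the running numbering of section 9.2) asks for a documented diagnosis and mentions no date. The date is listed in Table 1 of protocol 9.3 as a history item, "Date of COPD diagnosis (years from diagnosis". On missing data, protocol 9.7 says: "Patients with missing values will not be excluded from the analysis, their data will not be replaced". Section 9.13 repeats this.

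SAP section 4 foresees gaps ("If the investigator is unable to collect the requested information the data will be" NK or NA). Its general rule takes a patient out only of summaries of the variable that is missing.

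**The concern.** Criterion 2 tests only whether the date field is filled, not what it contains. A blank field does not contradict the diagnosis; it leaves one background detail unrecorded. The SAP nevertheless gives it the same effect as a failed inclusion criterion, and the patient's valid TSQM-9 scores at all three visits are lost with it.

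Two things are at stake. The first is an avoidable selection rule on the primary analysis. Protocol section 7 says that disease duration influences how patients perceive satisfaction, so if dates are blank more often in long-standing disease, the removed patients could differ from those kept. The second is traceability. The SAP openly states its departure from protocol 9.7 on post-baseline covariates (section 4.9), but not this one. Baseline Tables 4 to 9 are computed on the FAS, so they do not show how patients left out of the FAS compare. The optional selection-bias check at the end of SAP 4.2 looks at the follow-up sets, not at patients kept out of the FAS.

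**Working it through.** **Where the date is used**

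- SAP section 3: COPD duration and age at COPD diagnosis.
- SAP 4.2: both appear only in Table 6.
- TSQM-9 scoring (section 3), the regression covariates (section 4.9) and the resource-use counts do not use it.

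**What a blank diagnosis date does**

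- FAS, 6-month set and 12-month set: patient removed.
- SAP Tables 1 to 3: patient still counted, because percentages are over all enrolled patients.
- Safety set (SAP 2.4): not affected. It uses inclusion criteria 4 and 5 and patients "not meeting the exclusion criteria #7, #8 and #9". Criterion 2 is not among them.

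**Therapy start date, for comparison**

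- Criterion 8 requires "COPD Pharmacological therapy form: Start date of therapy (dd/mm/yyyy) (earliest record) not missing AND" an unticked deviation.
- Criterion 4 already requires "COPD Pharmacological therapy form: Start date of therapy (dd/mmm/yyyy) not missing AND" a check against the enrolment date.
- A patient who meets Criterion 4 has a dated therapy record, so the date condition in Criterion 8 removes nobody further. Changing Criterion 8 alone would re-admit nobody.

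**Reproducing the protocol's precision (section 9.5, Table 2, SD 21.4)**

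- Half-width = 1.96 × SD / √N.
- N = 380: 1.96 × 21.4 / √380 = 2.152.
- N = 320: 1.96 × 21.4 / √320 = 2.345.
- Both agree with the protocol.

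**Effect on the mean (illustration)**

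Let p be the share removed, K the mean of those kept and R the mean of those removed. The full mean is (1 − p)K + pR, so the reported mean K is off by p(K − R). The documents give neither p nor K − R; both are assumed.

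- p = 5%, K − R = 5 points: 0.05 × 5 = 0.25 points.
- p = 10%, K − R = 5 points: 0.10 × 5 = 0.5 points.
- Relative to the half-width: 0.25 / 2.345 = 11% to 0.25 / 2.152 = 12%, and 0.5 / 2.345 = 21% to 0.5 / 2.152 = 23%.

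**Effect on precision**

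The protocol's 5% to 20% loss already includes non-evaluable patients. If blank dates were the only loss from 400, 5% or 10% would leave 380 or 360, inside the planned 320 to 380. At 360 the half-width is 1.96 × 21.4 / √360 = 2.211. Precision is not the issue; selection is.

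**The case against.** The best defence is that the SAP checks several eligibility answers against recorded data (age, consent dates, therapy dates), and that a month and year of diagnosis is a modest test of whether a diagnosis is documented. The protocol also limits analysis to patients without eligibility violations (sections 9.6 and 9.7), so its missing-values sentence can be read as applying only after that step. This carries weight for Criterion 4, where the start date is needed to verify three months of stable treatment. It carries little for Criterion 2: the value of the date is never examined, and the protocol criterion requires none, so a blank is not a violation.

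A second objection stands in part. SAP section 4 separates NK and NA from entries not recorded. Criterion 10 names the non-response code in addition to missing, while Criterion 2 names no code. A date coded NK may therefore not count as missing. The documents do not settle this. It narrows who is caught but leaves the defect for truly blank dates.

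Third, few dates may be blank. Protocol 9.4 expects the variables to be in the charts, and SAP section 6 describes edit checks and approval of data quality before lock. SAP Table 2 would also make the loss visible. All of this stands, and it limits the size of the point.

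**Conclusion.** The point holds for Criterion 2. A blank diagnosis date removes an investigator-confirmed patient from every table based on the FAS or its subsets, in conflict with the protocol's diagnosis criterion, its missing-data rule and the SAP's own general rule. The number affected is unknown and may be small. Under the assumed 5% or 10% removed and a 5-point difference, the mean shifts by 0.25 or 0.5 points.

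Three stronger readings are not supported:

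- **Criterion 8 does separate damage, including to the Safety set.** Criterion 4 already imposes the start-date requirement for both sets, and there the date has a real verification role.
- **The bias could match the half-width.** That takes 20% removed and a 10-point difference (0.20 × 10 = 2.0 points). Neither figure has a basis in the documents. Taking such a share off 380 also risks counting the non-evaluable patients twice.
- **The loss is known to be non-random.** The protocol links duration to satisfaction, but nothing in the documents links duration to blank dates. It is plausible, not shown.

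**What to change.** In SAP 2.1, delete the diagnosis-date condition from Criterion 2 and keep the investigator's answer and the deviation check. State that a blank or NK date affects only COPD duration and age at diagnosis in Table 6. Report the number of blank dates as missing data, not as a reason for non-eligibility in Table 2. The strict set can be run as a sensitivity analysis.

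If the handling of blank therapy start dates is also revisited, change Criteria 4 and 8 together and keep the verification of stable treatment in view.

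The cost is one line of SAP wording and a small programming change, with no new data. The small downside is that documentation of the diagnosis then rests on the investigator's answer and the deviation form.

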9.2 SETTING

A log of all patients included into the study (i.e. having given informed consent) will be maintained in the ISF at the investigational site.

Boehringer Ingelheim reserves the right to discontinue the study overall or at a particular study site at any time for the following reasons:

1. Failure to meet expected enrolment goals overall or at a particular study site
2. Any administrative reasons that could significantly affect continuation of the study according to signed site contract
3. Violation of GCP, the CTP, or the contract by a study site or investigator, disturbing the appropriate conduction of the study

The investigator / the study site will be reimbursed for reasonable expenses incurred in case of study termination (except in case of the third reason).

All patients, both female and male gender, referring to pulmonary centers will be consecutively enrolled according to the following criteria:

Inclusion Criteria

7. Patients aged ≥ 40 years
8. Patients must have a documented diagnosis of chronic obstructive pulmonary disease (COPD)
9. Patients with no exacerbations in the last 3 months
10. Patients requiring regular treatment according to GOLD guidelines, i.e.: undergoing stable pharmacological treatment for COPD since at least 3 months
11. Written informed consent to both participation in the study and privacy form
12. Patients capable of discernment and able to read or write in Italian language.

Exclusion Criteria

4. Patients who are currently participating in a clinical trial on experimental drugs.
5. Patients naïve to pharmacological treatment for COPD
6. Diagnosis of Asthma COPD Overlap Syndrome (ACOS)

Study Exit criteria

An individual patient may be withdrawn from the non-interventional study prior to completion if any of the following criteria apply:

4. The patient withdraws consent, without the need to justify the decision.
5. The patient is no longer able to participate (according to clinical judgment)
6. Administrative reasons (inclusion in another clinical trial)

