The patients switching treatment during observation period will not be excluded from analysis and will be evaluated at each visit as above described. Few patients are expected to stop treatment during study; if any, for primary objective evaluation they will be censored at the latest available visit. Comparisons of satisfaction between different treatment/devices are not matter of this study, throughout all analysis treatments will be lumped together.

Secondary objectives

#1 To describe patient disease perception (B-IPQ), adherence to COPD treatment (MMAS4), health status (CAT) and dyspnea (MMRC) during a 12-month observation period

A description of B-IPQ (consequences, timeline, personal control, treatment control, identity, concern, emotions and illness comprehensibility), MMAS-4, CAT and MMRC scores will be provided at baseline and at follow-up visits. Scale scores will be summarized at each time point. Patients lost to follow up will be considered until their last available visit. Missing items of questionnaires/scales will be replaced if applicable according to scoring algorithm [32-38].

#2 To analyse the relation between treatment satisfaction for medical treatment and demographic/clinical parameters and PROs during a 12-month observation period

Three regression models (one for each TSQM-9 domain score) will be estimated; the dependent variable will be domain score and the independent ones will be: age and gender (at enrollment), number of exacerbations, relevant spirometry parameters (such as FEV1, FVC, FEV1 % of the predicted, RV, TLC, DLCO), level of dyspnea (MMRC score), impact of COPD on a patient's life (CAT) and treatment adherence (MMAS-4 score) collected during observational period. Because dependent variable will be collected at each study visit, repeated measures models will be estimated taking into account all available values for dependent and independent variables. Patients could be classified in mild or moderate/severe according to lung function parameters. This will allow to evaluate treatment satisfaction in different groups of patients.

The patients switching treatment during observation period will not be excluded from analysis and will be evaluated at each visit. The patients stopping treatment during study will be censored at last available visit.

#3 To describe the health care resources utilization and related cost during a 12-month observation period

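### SAP 2.1 adds date checks under criteria 4 and 5 that can exclude patients who meet the protocol's inclusion criteria, and criterion 4 does not say which therapy records must pass

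*SAP*

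**What the plan says.** **Criterion 4 (SAP 2.1).** Besides the investigator's 'Yes' and no ticked deviation, therapy dates must pass two tests:

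- Start: more than 3 × 30.4375 days before enrolment, or after it: "OR Start date of therapy (dd/mmm/yyyy) > Date of enrolment visit (dd/mm/yyyy)) AND".
- End: "missing OR End date of therapy (dd/mmm/yyyy) > Date of enrolment visit (dd/mm/yyyy".

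No record is named, whereas criterion 8 specifies the earliest one. No restriction to COPD therapies is stated. SAP 3 shows that the same log also holds therapies for exacerbations and adverse events, and applies a COPD filter when it classifies treatments.

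**Criterion 5 (SAP 2.1).** "Date of informed consent signature (dd/mm/yyyy) = Date of privacy form signature (dd/mm/yyyy) AND". Protocol 9.2 asks for "Written informed consent to both participation in the study and privacy form" and says nothing about equal dates.

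**Criterion 10 (SAP 2.1).** It admits "patients with at least one Treatment Satisfaction Questionnaire for Medication (TSQM-9) domain score calculated at enrollment visit". Protocol 9.7 defines evaluable patients as "patients who enter the study without inclusion-exclusion criteria violations and with at least one TSQM-9 domain score", with no visit named.

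**Where the flags are used.** The 6- and 12-month sets (SAP 2.2, 2.3) are subsets of the FAS. The Safety set (SAP 2.4) also requires criteria 4 and 5.

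**The concern.** A date check that confirms eligibility should not reject someone who satisfies the criterion. The equal-date test rejects a patient who signed both forms on different days before enrolment. The strict inequalities reject therapy records dated on the enrolment day, when a physician may well change treatment. Protocol 9.7 wants such patients kept: "The patients switching treatment during observation period will not be excluded from analysis and will be evaluated at each visit as above described".

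Failing criterion 4 or 5 removes a patient from every visit of the primary tables (Tables 10 and 11) and from Tables 40 to 44, including the adverse event listing, although protocol 11.2 collects events from consent onwards. The quality check in SAP 6 compares the flags with the SAP's own algorithm, so it cannot reveal a mismatch with the protocol. Because no record rule is given, two programmers could also build different analysis sets from the same text.

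**Working it through.** **1. The plan's own figure.** Protocol 9.5 gives SD 21.4 and N = 380 or 320. Half-width = 1.96 × SD / √N: 1.96 × 21.4 / √380 = 2.152 and 1.96 × 21.4 / √320 = 2.345. Both match protocol Table 2.

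**2. Criterion 4, dates alone.** Count days from enrolment (day 0); 3 × 30.4375 = 91.3125. As written:

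- start passes if < −91.3125 or > 0
- end passes if missing or > 0

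Take a sole drug begun on day −700 and replaced on day d, so the records are A = (−700, d) and B = (d, missing). Run d from −365 to +365, which is 731 days. Taking three months as the SAP's 91.3125 days, the patient meets protocol inclusion 4 if d ≤ −92 (274 days) or d ≥ 0 (366 days), 640 in all. On the other 91 days (−91 to −1) the patient does not.

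**3. Add the investigator gate.** The date tests are joined by AND to the investigator's answer. With question 4 answered correctly, the 91 non-compliant days fail whatever the dates say.

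| Reading | Wrong fails | Wrong passes, dates alone | Wrong passes, question 4 answered correctly |
|---|---|---|---|
| Every record must pass both tests | 275 | 0 | 0 |
| One and the same record must pass both | 1 | 0 | 0 |
| Different records may pass each test | 0 | 91 | 0 |

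The single fail under the same-record reading is d = 0: A ends on day 0 and B starts on day 0, so neither record passes both tests. The 275 under the every-record reading are d = 0 plus 274 days (−365 to −92) on which the ended drug A fails the end test. Those 274 matter only if drugs ended before enrolment are logged; SAP 3 hints at this when it disregards switches before enrolment. These are counts of dates, not of patients.

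**4. Inclusive enrolment day.** With ≥ 0 in both tests, wrong fails become 274, 1 − 1 = 0, and 0 respectively. The remaining 274 need a stated record rule.

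**5. COPD filter.** Without it, under the every-record reading, a logged course for an adverse event that ended before enrolment fails the end test and excludes the patient, however stable the COPD treatment.

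**6. The cut-off.** A start 91 days before enrolment fails and one 92 days before passes. For enrolment days from November 2015 to June 2016, a start exactly three calendar months earlier fails on 120 of the 240 days that have a matching date.

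**7. Precision.** The documents give no exclusion rate. If 20 of 380 evaluable patients were lost (an assumption), the half-width is 1.96 × 21.4 / √360 = 2.211. A 10% loss (N = 342) gives 2.268.

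**The case against.** The best defence is that these checks make eligibility operational, that protocol 9.6 already removes violators, and that the rules are printed openly with reasons counted in SAP Table 2. The SAP also protects most switchers, since drugs begun or ended after enrolment pass. That is fair, but it does not cover a patient who violated nothing, and a count in Table 2 restores nobody.

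Several stronger readings are tempting and are not supported:

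- *No reading of criterion 4 reproduces the protocol.* This is true of the dates alone. With the investigator's answer correct, the different-records reading makes no error in the sweep.
- *The dates admit ineligible patients*, for example one whose only logged drug starts after enrolment. That patient enters only if the investigator also answered wrongly.
- *The revised rule is error-free.* The sweep borrows the SAP's 91.3125-day cut-off, so it cannot validate that cut-off.
- *The oxygen rule, which counts a start on the enrolment day, shows inconsistency.* It uses another form. For the drug log, SAP 3 is strict elsewhere too.
- *Criterion 10 contradicts the protocol.* Protocol 9.7 names no visit, so the SAP narrows it. The statement "Patients with missing values will not be excluded from the analysis, their data will not be replaced" can be read as covering only patients already evaluable.

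It could also be said that SAP 2.4 glosses the Safety set in words that mention no dates. But it cites the criteria by the SAP's own numbers, and those include the date tests.

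**Conclusion.** The point holds as a specification defect that should be corrected. Criterion 5 is stricter than the protocol without a stated reason. Criterion 4 fails enrolment-day records, so a visit-day replacement of a stable sole drug excludes the patient under the every-record and same-record readings. It is also incomplete on which records count. Under the every-record reading, ended earlier drugs would exclude too, if they are logged.

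The consequence concerns who is analysed, in the primary tables at every visit and in the safety tables. The number of patients and any bias cannot be derived from the documents, and the loss of precision is small under the ranges shown. Criterion 10 is a narrowing that needs a label. It affects only the follow-up score rows, because change from enrolment needs both scores anyway.

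**What to change.** Before the evaluability flags are run:

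1. **Criterion 5:** replace the equal-date test with each form dated on or before the enrolment visit.
2. **Criterion 4:** test only records whose 'Therapy for' field is COPD, use ≥ for the enrolment day in both tests, and state which records must pass. A record starting on or after enrolment should not qualify a patient alone. The sponsor should reconcile the record rule and the 91.3125-day cut-off with protocol inclusion 4; no definition of stable treatment is proposed here.
3. **Related definitions in SAP 3:** align enrolment-day handling in the ongoing-at-enrolment and switcher rules. Otherwise, for a visit-day replacement still running at the end of observation, the old drug is not counted as ongoing at enrolment and the patient has one qualifying record, so is classed as a non-switcher. Changing > to ≥ in the switcher rule does not cure this, because the old drug's record is still not counted; the intended class must be stated.
4. **Criterion 10:** state that it is narrower than protocol 9.7. Optionally, as a supportive analysis, repeat the 6- and 12-month score rows of Table 11 in eligible patients with a domain score at that visit.

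The cost is SAP text and program edits, with no new data. The analysis sets may grow or shrink, since the COPD filter and the record rule can remove patients as well as add them. The optional step produces two sets of rows twice, with slightly different denominators.
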